#### **5.5 Study Drug Treatment:**

Patients who meet eligibility criteria, provide informed consent and are enrolled in the study will receive instructions regarding resveratrol dosage, route and administration. A 8-week supply of resveratrol 250mg daily will be provided at visit 1. Patients will be reminded about the side effects of resveratrol, and will be given a drug information sheet. Patients will be instructed to take the study medication at the same time every day. Patients will be carefully monitored monthly at subsequent visits for adverse effects

related to resveratrol. Common side effects of resveratrol include nausea, vomiting, diarrhea, flatulence, abdominal discomfort, and fatigue. Patients will be instructed to contact the study staff should they experience any of these side effects. Resveratrol doses may be held or reduced in the event of unacceptable side effects.

### **5.6 Treatment Regimen:**

We have chosen an intra-patient dose escalation strategy because there is no previous data from human studies to demonstrate the safety of resveratrol in combination with sirolimus, in patients with LAM. Patients will begin resveratrol at a starting dose of 250mg daily, and increase the dose to 500mg daily after 8 weeks, followed by dose escalation to 1000mg daily in two divided doses (500 mg twice a day) at week 16 of the study. If no adverse effects are seen, patients should reach a dose of 1000mg per day at week 16 of the study, and then continue with this dose for the rest of the study duration. If patients do not tolerate a certain dose of resveratrol, the dose will be reduced to the last tolerated strength. Patients will remain on the last well-tolerated dose of resveratrol for the entire study duration. Patients will remain on their current dose of sirolimus without interruption, as clinically indicated. Patients who are unable to tolerate the lowest dose of resveratrol will be withdrawn from the study.

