## 6. Study Procedures and Timelines

### 6.1 Study and Timeline Overview

Patients will be identified by the medical and research staff at the LAM clinic at the University of Cincinnati Medical Center. Study staff will screen up to 60 patients over 15 months with a goal of enrolling 25 participants. Patients who meet eligibility criteria, provide informed consent and are enrolled in the study will receive instructions regarding resveratrol dosage, route and administration. An 8-week supply of resveratrol will be provided at visit 1. Patients will begin resveratrol at a starting dose of 250mg daily, and increase the dose in two increments to a maximum dose of 1000mg daily. If patients do not tolerate a certain dose of resveratrol, the dose will be reduced to the last tolerated strength. Patients will remain on the last well-tolerated dose of resveratrol for the entire study duration. Patients who are unable to tolerate the lowest dose of resveratrol will be withdrawn from study.

The patients will be given a copy of the informed consent form. Patients will be given ample time to read and discuss the consent form with the study staff. The study staff will then answer any remaining questions asked by the patients. The patients will be offered the option of signing the consent form. Those who agree to participate will undergo the remainder of screening visit.

Prior to starting study drug, pre/post bronchodilator spirometry, diffusion capacity of carbon monoxide (DLCO), and serum VEGF-D will be obtained to establish baseline values prior to study drug initiation. The best values for FEV1 and FVC obtained during the spirometry maneuvers will be used. Patients will be followed with serial spirometry and VEGF-D levels collected at the initial visit, followed by week 8, week 16 and week 24 visits. DLCO will also be obtained at the 24-week visit in addition to spirometry.

For patients who agree to the home spirometry study, we will teach them on the proper technique to perform, record and transmit home spirometry, and provide them with a home spirometer. The patients will perform their first test during the initial visit and we will use those values to compare the home spirometer values with the office-based spirometry values. After that patients will be instructed to perform home spirometry once a week as detailed in Section 5.7.

Section 6.2 provides a summary of the study timeline and procedures.

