#### **6.5 Patient retention and drug compliance**

Patient retention will be encouraged in several ways. Extensive contact information will be captured for each patient, at the time of study enrollment. This will include home, work, and cellular telephone numbers and that of an emergency contact or nearest family member. Prior to each study visit, the study staff will contact the patient to remind her about the upcoming study visit. A check for the reimbursement of expenses up to \$500 will be issued after each study visit.

The study staff and physician will explain the importance of compliance with the study protocol at each patient contact. If a patient fails to comply with a study visit, the study staff will contact her by telephone. If the study staff is unsuccessful in reaching the patient, a follow up letter will be sent by overnight carrier, on two consecutive weeks, seeking follow-up.

Compliance with the protocol and drug administration will be strongly emphasized. Pill counts will be performed at visits and episodes of medication noncompliance will be recorded, including the reason for noncompliance. Patients will receive a calendar to document medication and any side effects experienced that day. If a patient wishes to withdrawal from the treatment phase of the study or has a serious adverse event (SAE) (whether related to study drugs or not), patient follow-up assessments will continue for safety monitoring and to avoid problems associated with missing data. The inclusion of such follow-up data will allow for analysis by intention-to-treat.

If a patient is withdrawn from study drug exposure for any reason, the patient will be strongly encouraged to continue with and complete the remainder of the study assessments, as scheduled.

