### 12.3.2 Resveratrol dose reduction

Any AE of  $\geq$  Grade 3 and attributed as possibly, probably or definitely related to resveratrol will result in the dose being held until the AE has resolved to  $\leq$  grade 1 or baseline, while sirolimus dosing may continue uninterrupted. If the AE resolves, reinstitution of treatment can occur but at a reduced dose as described in Table 3. If the AE recurs at the reduced dose, treatment will be held until the AE has resolved to  $\leq$  grade 1 and when resolved treatment can be reinstated at the next lower dose level. No more than 2 dose reductions are allowed during the maintenance cycles. Participants who are unable to tolerate the lowest dosage of resveratrol will be withdrawn from study drug exposure.

Toxicities that may be attributable to resveratrol include nausea, vomiting, abdominal pain, diarrhea, headache, and fatigue. If any of these AEs occur at grade  $\leq$  2, resveratrol may be continued and the AE managed with supportive care. For any AE with a grade  $\geq$  3, the rules outlined in Sections 14.2 – 14.10 apply for holding of dose, dose reduction, removal from study and reporting requirements.

Dose	Reduce to
250 mg daily	Hold or withdrawal from resveratrol exposure
500 mg daily	250 mg daily
1000 mg daily	500 mg daily

**Table 3:** Dose reduction schema for resveratrol

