#### **13.1.4 Individual early stopping rules**

A study participant will be terminated from the study if any of the following occurs during the study:

- Recurrent or persistent resveratrol-related toxicity unresponsive to treatment in spite of dose adjustments.
- Pregnancy or failure to comply with adequate contraception
- The participant refuses to continue in the study
- Continued non-compliance
- The investigator determines that the participant should be withdrawn from the study for reasons not listed above

A subject will be considered evaluable if they receive treatment for at least 8 weeks and the relevant information collected during this period. Subjects who are withdrawn after less than 8 weeks of treatment will be considered as pre-mature discontinuation, and will be replaced by another participant.

Every effort will be made to obtain endpoint evaluations for subjects who withdraw or who discontinue prematurely from the study. The same evaluations performed at final visit will be completed at the time of termination. If withdrawal is due to inability to tolerate investigational drug or other untoward event related to investigational drug, the withdrawal will be noted in data analysis as treatment failure.

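### For a patient who cannot tolerate 250 mg, sections 5.6 and 6.1 end study participation, section 12.3.2 ends resveratrol only, and no rule says how she enters the week-24 VEGF-D test

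*Combined protocol and SAP*

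**What the plan says.** Section 5.6 (Treatment Regimen): "Patients who are unable to tolerate the lowest dose of resveratrol will be withdrawn from the study". Section 6.1 repeats it: "Patients who are unable to tolerate the lowest dose of resveratrol will be withdrawn from study". Section 13.1.4 points the same way for a related but not identical trigger, listing among the reasons for terminating a participant from the study: "Recurrent or persistent resveratrol-related toxicity unresponsive to treatment in spite of dose adjustments".

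Section 12.3.2, which governs resveratrol dose reduction, says instead: "Participants who are unable to tolerate the lowest dosage of resveratrol will be withdrawn from study drug exposure". The 250 mg row of its Table 3 reads "Hold or withdrawal from resveratrol exposure". Section 6.5 adds that, after withdrawal from study drug for any reason, "the patient will be strongly encouraged to continue with and complete the remainder of the study assessments, as scheduled". On retaining follow-up after treatment withdrawal it says: "The inclusion of such follow-up data will allow for analysis by intention-to-treat".

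Four other rules bear on what happens next:
- Section 13.1.2 keeps all data acquired before termination in the primary analysis unless consent is withdrawn.
- Section 13.1.4 asks for the final-visit evaluations at the time of termination. For withdrawal through drug intolerance, "the withdrawal will be noted in data analysis as treatment failure".
- Sections 13.1.4 and 13.3 treat a patient with less than 8 weeks of treatment as non-evaluable and replace her.
- Section 15 places everyone who receives study drug in the efficacy set. It tests VEGF-D after 24 weeks against the pre-enrolment value with a paired t-test.

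**The concern.** Leaving the drug and leaving the study are different events for the analysis. A patient who only leaves the drug can still supply a week-24 VEGF-D; one who leaves the study before week 24 cannot. The protocol assigns both outcomes to the same patient and gives neither text precedence.

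At stake is selective loss from the primary comparison. If intolerant patients respond less than others and have no week-24 value, the paired test describes a slightly more favourable group than the efficacy set that section 15 defines.

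There is also a practical side. Section 14.12.1.2 gives, as an example of a major deviation, a subject who met withdrawal criteria but was not withdrawn. A coordinator who follows section 6.5 and keeps the patient to week 24 could be recorded as breaching section 5.6. One who follows section 5.6 ends the visits that section 6.5 wants.

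**Working it through.** **Step 1: the texts side by side.**

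| Section | Trigger | Consequence |
|---|---|---|
| 5.6, 6.1 | cannot tolerate lowest dose | out of the study |
| 12.3.2, Table 3 | cannot tolerate lowest dose | off resveratrol |
| 13.1.4 | persistent resveratrol toxicity despite dose adjustment | out of the study |
| 6.5 | off study drug for any reason | encouraged to complete scheduled assessments |

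The first two rows share a trigger and differ in consequence.

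**Step 2: follow one patient.** Under sections 5.6 and 6.1, her scheduled visits end. She has a baseline VEGF-D, any week-8 or week-16 value already taken, and a termination evaluation at whatever date she leaves. Section 15 does not say whether the termination value stands in for week 24, or how the treatment-failure label enters a test on a continuous outcome. Under sections 12.3.2 and 6.5, she is asked to attend week 24, when the section 6.2 schedule includes VEGF-D.

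**Step 3: add the timing.** Every patient takes 250 mg in weeks 0 to 8 (section 5.6), so most intolerance of that dose should show then. Evaluability in section 13.1.4 depends on having at least 8 weeks of treatment. A patient who stops at week 3 is therefore non-evaluable and replaced, even if the drug-only wording is adopted. That protects the count of 20 evaluable subjects but conflicts with an efficacy set of everyone dosed. Later cases, such as stepping down from 500 mg and then failing 250 mg, escape the replacement rule but meet the conflict in Step 1.

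**Step 4: scale.** No rate of 250 mg intolerance is given, so this is illustration only.

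The design figure first (section 15: difference 420 pg/ml, n = 20, correlation 0.7, SD 800). If 800 is the SD at one visit, the SD of the difference is 800 × √(2 × (1 − 0.7)) = 619.7. Exact two-sided paired-t power at n = 20 is then 0.820, and 20 / (1 − 0.20) = 25 recruited. Taken literally as the SD of the difference, 800 gives power 0.606. That discrepancy is a separate matter, and both values are used here only to set a scale: SE = 619.7/√20 = 138.6, or 800/√20 = 178.9.

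Let k of D dosed patients be lost for 250 mg intolerance. Assume a mean fall of e among them and 420 among the rest. The mean without them exceeds the mean of all dosed patients by

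gap = (k/D) × (420 − e).

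Section 7.2 enrols up to 25, and the plan does not say whether replacements come on top, so D is taken as 25 and as 25 + k.

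| k | e | D = 25 | D = 25 + k |
|---|---|---|---|
| 1 | 0 | 420/25 = 16.8 (16.8/403.2 = 4.2%) | 420/26 = 16.2 (16.2/403.8 = 4.0%) |
| 3 | 0 | 1260/25 = 50.4 (50.4/369.6 = 13.6%) | 1260/28 = 45.0 (45.0/375.0 = 12.0%) |
| 1 | 210 | 210/25 = 8.4 (8.4/411.6 = 2.0%) | 210/26 = 8.1 (8.1/411.9 = 2.0%) |
| 3 | 210 | 630/25 = 25.2 (25.2/394.8 = 6.4%) | 630/28 = 22.5 (22.5/397.5 = 5.7%) |

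Gaps are in pg/ml; percentages are of the all-dosed mean. With e = 0, one patient moves the estimate by 16.2/178.9 = 0.09 to 16.8/138.6 = 0.12 SE, and three by 45.0/178.9 = 0.25 to 50.4/138.6 = 0.36 SE.

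**The case against.** The strongest reply is that the detailed text already resolves this. Section 12.3.2 is the operative dose-reduction section, section 6.5 covers withdrawal from drug for any reason, and sections 12.3.1 and 13.2 also speak of withdrawal from drug exposure. Sections 5.6 and 6.1 are single sentences in a regimen description and an overview. This has weight, and it makes the drug-only reading the likelier intention. It does not remove the conflict, because nothing gives those sections precedence and section 13.1.4, with section 7.1(g), supports study termination.

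A reader might infer that intolerant patients are barred from the primary analysis. The documents do not say so. Section 13.1.2 retains data acquired before termination for the primary analysis, section 13.1.4 seeks endpoint evaluations from those who withdraw, and section 15 plans mixed models that can use week-8 and week-16 values. What is missing is a rule for how such values enter the paired t-test.

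A reader might also infer that the result would describe only patients who tolerate full dosing. It would not: those who fail 500 or 1000 mg step down and stay in the study. Only 250 mg intolerance is at issue.

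The treatment-failure label need not be a defect, since a descriptive flag would satisfy the wording.

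Finally, intolerance may be rare. Section 9.1.2 reports no resveratrol-related adverse effects in studies of up to 1 gram per day. Section 5.6, however, notes that there are no human safety data for the combination with sirolimus in LAM, so a rate of zero cannot be assumed.

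**Conclusion.** Minor, but wrong as written: the stated rules conflict, and under one of them the week-24 VEGF-D is not collected from patients who cannot tolerate 250 mg. The 8-week replacement rule adds to the selection and would remain after the wording in sections 5.6 and 6.1 is aligned, so alignment alone does not settle the matter.

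The effect on the estimate is unknown and probably small. The illustrated shifts rest on assumed counts of one to three such patients, an assumed zero or half response among them, and the planned 420 pg/ml in everyone else. If the drug is inactive in intolerant and tolerant patients alike, their loss does not create an apparent effect; the risk is modest overstatement of a real one. Power is not the main concern, since the plan allows for 5 of 25 lost and replaces early stoppers.

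**What to change.** 1. In sections 5.6 and 6.1, use the section 12.3.2 disposition, withdrawal from study drug only. In section 13.1.4, make the resveratrol-toxicity bullet a reason to stop resveratrol, with the remaining week 8, 16 and 24 assessments continued under section 6.5. Leave the other withdrawal reasons unchanged.
2. In sections 13.1.4, 13.3 and 15, state that a patient who stops before 8 weeks may be replaced for accrual but stays in follow-up and in the efficacy set of all dosed subjects.
3. In section 15, state that observed week-24 VEGF-D from patients off drug is used in the primary analysis. For patients who decline further visits, enter the termination value in the planned mixed model at its actual date, not relabelled as week 24. Report treatment failure as a descriptive count.

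The cost is wording changes in sections 5.6, 6.1, 13.1.4 and 13.3 and three short rules in section 15. A few already scheduled visits would take place in patients off drug, and the estimated effect may be slightly smaller. No new procedures are needed.

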### **5.7 Home Spirometry**

We will provide patients with a home spirometer (GoSpiro, Monitored Therapeutics Inc.) at the beginning of the study. This device was chosen after a careful survey of 9 different home spirometers, based on its ability to assess acceptability and reproducibility of maneuvers and fully comply with the ATS/ERS standards of a spirometer (38). FEV1 and FVC will be obtained once weekly from patients agreeing to participate in the home spirometry sub study. Detailed instructions regarding the proper use of the home spirometer will be provided at the time of enrollment, along with access to detailed instruction manuals for future use. Once a week, patients will perform at least three spirometric measurements at approximately the same time, and record the best FEV1 and FVC values as their weekly results. Patients will also be asked to complete a brief survey to rate their experience with the home spirometry every week. These results, along with the associated flow-volume and volume-time loops will then be transmitted electronically to the study coordinator. The spirometric values as well as the loops will be reviewed in near real time along with direct feedback to the subject on the performance and trouble shooting of any issues by an expert pulmonary physiologist ([name] and/or [name]). The spirometry data and loops will be judged for their acceptability and reproducibility as specified in the ATS/ERS guidelines (38). A maneuver will have to satisfy both the satisfactory start as well as end of test criteria in order for it to be considered acceptable. Difference between the largest recorded FEV1/FVC and the next largest FEV1/FVC less than 150ml will determine satisfactory intra-test reproducibility. Inter-test reproducibility will be assessed by comparing the FEV1 values obtained during the first 4 weeks of home spirometry measurements, with a target between-test variation of less than 5%. Overall compliance to weekly home spirometry will be recorded with

success defined as greater than 80% compliance with weekly measurements throughout the 24-week study duration.

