Study Procedures	
The primary objective of this trial is to evaluate the change in serum VEGF-D after 24 weeks of combined resveratrol and sirolimus as compared to the baseline serum VEGF-D value on sirolimus alone. Secondary objectives include an assessment of the safety and tolerability of resveratrol in combination with sirolimus in patients with LAM, as well as the effect of combined resveratrol and sirolimus on lung function and quality of life. The frequency, severity and duration of all adverse events, regardless of cause, will be tabulated by body system and by severity using the NCI Common Terminology Criteria for Adverse Events v4.0. Subjects will have a medical history, physical examination, and laboratory measurements of complete blood count, renal and liver function tests, serum VEGF-D, and sirolimus levels drawn at every in-person visit. Pre and post bronchodilator spirometry measurements will be performed at each visit. St. George's respiratory questionnaire (SGRQ), SD-SB, EuroQOL and ATAQ LAM will be used for quality of life assessment, and these questionnaires will be filled out at each in-person study visit.
 
Patients enrolling in RESULT will be trained on proper technique for home spirometry using an advanced vertical turbine based device that records and wirelessly transmits full flow volumes loops. Once a week, patients will perform at least three spirometry maneuvers that pass ATS/ERS acceptability criteria and choose the best value as their weekly FEV1 and FVC. All spirometric data will be reviewed by an expert pulmonary physiologist, who will judge the spirometry data and loops for intra-test acceptability and reproducibility as specified in the ATS/ERS guidelines, as well as provide near real time electronic feedback to patients regarding their technique. We will correlate spirometry values and trends (absolute as well as rate of decline) obtained from weekly home spirometry with the office-based spirometry values, as well as serum VEGF-D, and quality of life assessment scores.

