## 2. Glossary of Abbreviations

AE	Adverse event
AEDAMS	Adverse Event Data Management System
AMPK	5' AMP-activated protein kinase
ATAQ-LAM	A Tool to Assess Quality of Life in LAM
ATS	American Thoracic Society
AUC	Area under the curve
BD	Bronchodilators
CAPA	Corrective and Preventative Action
CBC	Complete blood count
CFR	Code of Federal Regulations
cGCP	Current Good Clinical Practice
Cmax	Peak plasma concentration
CMP	Comprehensive metabolic panel
CRF	Case report form
CT	Computerized tomography
CTCAE	Common Terminology Criteria for Adverse Events
CYP	Cytochrome P450
DLCO	Diffusion capacity for Carbon Monoxide
DSMB	Data Safety Monitoring Board
DSMP	Data Safety Monitoring Plan
ERS	European Respiratory Society
eCRF	Electronic Case Report Form
Evaluable Patients	Patients whose response to a treatment can be measured because enough information has been collected
FDA	Food and Drug Administration
FEV1	Forced expiratory volume in first second

FVC	Forced vital capacity
FPI	Functional Performance Inventory
GEE	Generalized Estimating Equations
HIPAA	Health Insurance Portability and Accountability Act
HRCT	High-resolution computed tomography
ICH	International Conference on Harmonization
IND	Investigational New Drug
IRB	Institutional Review Board
LAM	Lymphangioleiomyomatosis
MEF	Mouse epithelial fibroblasts
MILES	Multicenter International LAM Efficacy of Sirolimus
mTOR	Mammalian Target of Rapamycin
NCI	National Cancer Institute
NIH	National Institutes of Health
NSAES	Non Serious Adverse Events
OHRP	Office for Human Research Protection
PFT	Pulmonary function test
PI	Principal Investigator
SAE	Serious Adverse Event
SAR	Suspected Adverse Reaction
SD-SOB	San Diego Shortness of Breath Scale
SGRQ	St. George's Respiratory Questionnaire
SUSAR	Suspected, Unexpected Adverse Reaction
TSC	Tuberous Sclerosis Complex
Tmax	Median time to achieve peak plasma concentration
TUNEL	Terminal deoxynucleotidyl transferase dUTP nick end labeling
VEGF-D	Vascular Endothelial Growth Factor - D

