**Home spirometry evaluation:** The spirometry values will be expressed as mean  $\pm$  SD. All spirometry maneuvers will be checked for acceptability and reproducibility as specified in the ATS/ERS criteria (38) by an expert pulmonary physiologist. The spirometry values obtained from maneuvers that do not satisfy the ATS/ERS criteria for acceptability will not be used in the primary analysis. If spirometric values meet the acceptability criteria but fail to satisfy the repeatability criteria, those values will be graded for quality, but will be used in the primary analysis. Overall compliance with weekly home spirometry will be recorded and reported as a percentage. Comparison of home spirometry and office-based spirometry values will be performed using the Bland-Altman method at baseline, and at each time frame that patients get an office-based spirometry (i.e. every 8 weeks). Rate of change of FEV1 (slope) over time will be calculated by using all available values (without imputations) in a linear mixed effects model after considering the correlation of the observations within each subject, and the time between measurements will be treated as a fixed effect. In order to analyze if the trends obtained from short-term follow up with frequent home spirometry correlate with overall disease trajectory, we will compare the rate of decline obtained after 8 weeks of home spirometry to the overall rate of decline obtained after 24 weeks of follow up. A similar analysis plan will be employed for serum VEGF-D, and other biomarkers. All statistical analyses for this study will be performed using SAS, version 9.4 (SAS Institute Cary NC).

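### The home-spirometry rule discards an FEV1 already complete at one second when the maneuver later fails end of test; FEV1 and FVC should be judged separately

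*Combined protocol and SAP*

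**What the plan says.** Section 5.7 (Home Spirometry) defines acceptability once per maneuver: "A maneuver will have to satisfy both the satisfactory start as well as end of test criteria". Section 15, under the home spirometry evaluation, states the consequence: "The spirometry values obtained from maneuvers that do not satisfy the ATS/ERS criteria for acceptability will not be used in the primary analysis". The Data Analysis part of the synopsis has the same sentence. None of these places treats FEV1 differently from FVC. The glossary expands FEV1 as "Forced expiratory volume in first second".

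Repeatability is handled more leniently. Section 15 keeps values that fail only on that count: "If spirometric values meet the acceptability criteria but fail to satisfy the repeatability criteria, those values will be graded for quality, but will be used".

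The weekly session is described in two ways. In section 5.7, "patients will perform at least three spirometric measurements at approximately the same time, and record the best FEV1 and FVC values as their weekly results"; the footnote to the section 6.2 schedule and section 8.5 agree. In the synopsis (Study Procedures), "patients will perform at least three spirometry maneuvers that pass ATS/ERS acceptability criteria and choose the best value as their weekly FEV1 and FVC". The first asks for three measurements of any quality, the second for three that pass. Section 5.7 has the patient record the best value before the expert reads the loops. No section says whether a rejected best value is replaced by the next acceptable one or the week is left missing.

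**The concern.** A blow with a good start that stops too early has a valid FEV1 and an invalid FVC. A single verdict removes both. FEV1 is the variable named for the slope model in section 15 and for the four-week inter-test reproducibility check in section 5.7. The 8-week versus 24-week comparison of decline and the Bland-Altman comparison with office values use the same maneuvers. Whether short, frequent home monitoring can recover the lung-function trajectory is the hypothesis stated in section 3.6, so losing usable FEV1 readings weakens the substudy where it matters most.

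There is a possible second effect. If failed blows are not repeated, the weekly FEV1 becomes the best of one or two blows instead of three, and a maximum over fewer draws is lower on average. If the share of failed blows changed during follow-up, part of that change would appear as FEV1 slope.

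**Working it through.** **The rule.** Take a maneuver with a satisfactory start that ends early, after the first second. Section 5.7 makes it unacceptable. Section 15 therefore excludes its values, including an FEV1 that was complete before the fault. This step needs no assumption.

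**Inputs for the size.** The plan gives no failure rate and no within-session SD, so there is no stated figure to reproduce. Assumptions:
- exactly three blows a week, all with good starts (the minimum under sections 5.7, 6.2 and 8.5);
- a fraction e of blows fails end of test only, independently of each other and of FEV1;
- within-session SD of FEV1 of 50-75 ml, normally distributed;
- the best remaining acceptable blow becomes the weekly value.

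**Formula.** The expected maximum of k normal draws, in SDs above the patient's mean, is 0 for k = 1, 1/√π = 0.5642 for k = 2 and 3/(2√π) = 0.8463 for k = 3. The number of accepted blows is Binomial(3, 1−e), and a week with none is missing (probability e³). So

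bias = [P(2) × 0.5642 + P(3) × 0.8463] / (1 − e³) − 0.8463.

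At e = 0.2: (0.384 × 0.5642 + 0.512 × 0.8463) / 0.992 − 0.8463 = 0.6552 − 0.8463 = −0.1911 SD.

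| e | bias (SD) | at SD 50 ml | at SD 75 ml | weeks with no FEV1 |
|---|---|---|---|---|
| 10% | −0.0915 | −4.6 ml | −6.9 ml | 0.1% |
| 20% | −0.1911 | −9.6 ml | −14.3 ml | 0.8% |
| 30% | −0.2922 | −14.6 ml | −21.9 ml | 2.7% |
| 50% | −0.4836 | −24.2 ml | −36.3 ml | 12.5% |

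**Slope.** With e constant, the bias is the same every week and the slope bias is 0. As an illustration of drift, let e fall linearly from 50% to 20% over weeks 0-24. The least-squares slope of the weekly bias is then +0.294 SD per 24 weeks, or +15 to +22 ml. If e rises from 20% to 50% instead, the sign reverses. If the whole fall occurs in the first 8 weeks, the 8-week slope gains 0.293 SD per 8 weeks (+15 to +22 ml per 8 weeks), while the 24-week slope gains 0.239 SD per 24 weeks (+12 to +18 ml per 24 weeks). The 8-week versus 24-week comparison is therefore the analysis most sensitive to drift.

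**Synopsis wording.** If blows are repeated until three pass, the weekly FEV1 is the best of at least three accepted blows. Relative to a best of three, the low bias and the slope artefact are both 0. Valid FEV1 readings from the failed blows are still discarded.

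**After the fix.** For faults confined to end of test, all three blows stay eligible for FEV1. The bias, the slope artefact and the lost weeks are then 0 under the same assumptions.

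**The case against.** The strongest reply is that one strict verdict is a defensible, conservative choice for unsupervised tests, and that little harm is shown. Several parts of it stand.

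- A reader might infer that weekly FEV1 will be biased low. The documents do not support that as stated. The synopsis asks for three passing maneuvers, sections 5.7, 6.2 and 8.5 set three as a minimum, and the device was chosen partly because it can assess acceptability. If a rejected best value simply left the week missing, there would be no downward shift of this kind either.
- A reader might infer that the planned technique feedback will raise the FEV1 slope. Nothing in the documents says the end-of-test failure rate will change. Patients are trained and perform a first test at the initial visit.
- A reader might infer that losses concentrate in sicker patients. No passage addresses this.
- A reader might infer a shift in the Bland-Altman bias. Section 8.2 holds office tests to ATS/ERS criteria too, so a shift requires the failure rate, or the way the criteria are applied, to differ between home and office.
- The amounts are modest beside the plan's own yardsticks: a 150 ml intra-test tolerance and a 5% inter-test target in section 5.7.

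What does not stand is the defense that citing the ATS/ERS guideline settles the matter. How that guideline treats FEV1 from an early-ended blow cannot be checked here, and section 5.7 states its own two-part test with no FEV1-only category. Nor does strictness explain why acceptable but non-repeatable values are kept while an FEV1 from a blow with a sound start is dropped.

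**Conclusion.** The defect is real: as written, the plan excludes valid FEV1 readings for faults that affect only FVC. The loss reaches the home-spirometry slope, 8-week versus 24-week, Bland-Altman and four-week reproducibility analyses. How much is lost depends on a failure rate the plan does not give.

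Bias is a conditional addition. With exactly three blows and substitution of the best remaining one, it runs from about 5 ml (10% failures, SD 50 ml) to about 36 ml (50% failures, SD 75 ml) downward. It reaches the slope only through drift in the failure rate, and it is zero under the synopsis wording. The documents do not settle which description of the session governs.

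The scope is narrow: an opt-in substudy (section 6.9) feeding secondary endpoints (section 4.2, items 12 and 13). The VEGF-D primary endpoint, safety and office lung-function endpoints are untouched. The change is worth making because it is cheap, not because the trial's main conclusion is at risk.

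**What to change.** In section 5.7, section 15 and the synopsis:

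1. Judge acceptability for each measure. FEV1: satisfactory start and no artefact through the first second. FVC: satisfactory start and satisfactory end of test.
2. Define weekly FEV1 as the largest FEV1 among FEV1-acceptable maneuvers, and weekly FVC as the largest FVC among FVC-acceptable maneuvers. A rejected best value is then replaced by the next acceptable one.
3. Run the FEV1 slope, 8-week versus 24-week, Bland-Altman and four-week reproducibility analyses on the FEV1-acceptable set. Report the both-criteria version as a sensitivity analysis.
4. Reconcile the synopsis with sections 5.7, 6.2 and 8.5 on whether the three weekly maneuvers must be acceptable, and report the number of acceptable maneuvers per week for each measure.

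The cost is revised wording and two flags per maneuver instead of one, from loops the physiologist already reads. No extra tests or staff are needed. The small downside is that FEV1 and FVC for a week may come from different numbers of blows. If sessions run until three maneuvers pass in full, FEV1 may be the best of more than three: going from three to four raises the expected best by 1.029 − 0.846 = 0.183 SD, which is why the count should be reported.
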